[name]. She holds a degree in business engineering, where she completed courses on General Statistics, Statistical Modelling and Data Mining, Econometrics, Algorithms and Data Structures, Simulation Modelling and Analysis, and Programming in JavaScript. In 2021, she completed an online Biostatistics course at KU Leuven and obtained certification through examination. Furthermore, she attained a certificate in Introduction to R organized by the FLAMES training network. In her doctoral research, [name] has undertaken several projects in health economics, resulting in first-author publications. Additionally, she conducted a budget impact analysis commissioned by the Flemish government, including a Python simulation model, which contributed to an additional allocation of 270 million euros to the Flemish childcare sector. As a final-year PhD candidate, [name] has extensively engaged with relevant literature and has actively participated in various international conferences focusing on health economic analyses.

Inclusion and exclusion criteria

Practices' eligibility (and physicians within these practices) for inclusion in the study will be based on the following criteria:

- Being able to recruit acutely ill children, ideally consecutively.
- Agree to the terms of the clinical study agreement.

Practices will be excluded from study participation based on the following criteria:

- Current use of a POC CRP device as part of their routine care

Age, demographics, geographic region will not be used to exclude eligible practices. This will provide us with a real-life, representative subset of ambulatory care physicians.

Patients' eligibility for inclusion in the study will be based on the following criteria:

- Children aged 6 months to 12 years, provided informed consent can be obtained
- Presenting with an acute illness episode that started maximum 10 days before the index consultation

Patients will be excluded from study participation based on the following criteria:

- Children who were previously included in this trial
- Children with an underlying known chronic condition (e.g., asthma, immune deficiency)
- Clinically unstable warranting immediate care
- Immunosuppressant medication taken in the previous 30 days
- Trauma as the main presenting problem
- Antibiotics taken in the previous 7 days
- Unwillingness or inability to provide informed consent

Endpoints and covariates

Endpoints

The primary outcome is the proportion of subjects who were prescribed antibiotic treatment (both immediate and delayed) at the index consultation as recorded by the treating physician.

Secondary endpoints:

- The duration (in days) until reaching full clinical recovery
- The proportion of subjects receiving additional testing (including, but not limited to (X-Ray, blood tests, urine tests) at index consultation (day 0) and/or during follow-up (day 1 to day 30)
- The proportion of subjects who re-consulted their physician during follow-up (day 0 to day 30)
- The proportion of subjects who were prescribed antibiotic treatment during follow-up (immediately after index consultation to day 30)

Exploratory endpoints:

- The proportion of subjects receiving additional testing (including, but not limited to (X-Ray, blood tests, urine tests) at index consultation (day 0)
- The proportion of subjects receiving additional testing (including, but not limited to (X-Ray, blood tests, urine tests) during follow-up (day 1 to day 30)
- The proportion of subjects referred to hospital at index consultation (day 0)
- The proportion of subjects referred to hospital during follow-up (day 1 to day 30)
- The proportion of subjects admitted to hospital at index consultation (day 0)
- The proportion of subjects admitted to hospital during follow-up (day 1 to day 30)
- The proportion of subjects who died at index consultation (day 0)
- The proportion of subjects who died during follow-up (day 1 to day 30)
- The proportion of subjects with full clinical recovery at day 7
- The proportion of subjects with full clinical recovery at day 30
- Patient's satisfaction (as part of the nested qualitative study)
- Parent's satisfaction (as part of the nested qualitative study)
- Physician's satisfaction (as part of the nested qualitative study)

- Cost-effectiveness of the intervention: healthcare expenditures in terms of hospitalization, consultations, pharmaceuticals (reimbursed and non-reimbursed), productivity, quality of life
- Adherence to the diagnostic algorithm
- The proportion of subjects who actually took antibiotics (from day 0 to Day 30)

Covariates (predictors in the model)

Important predictors were chosen a priori based on expert opinion by [name] [name].

Predictor	Measurement scale	Df needed
Study arm	Binary: intervention versus control	1
Age	Continuous	1

Handling of missing values and other data conventions

1. REDCap Data

Drop-outs are unlikely to be a large problem since there will be only one study visit complemented by the collection of follow-up information.

We will analyse the whole population for the primary analysis and perform a sensitivity analysis excluding the low recruiting practices (less than 10 patients recruited for 12 months) to avoid our results to be susceptible to selection bias. In previous trials this resulted in approximately 10% of practices.

Practices that do not recruit children at all will be stopped after the first two monitoring visits and replaced by new practices to avoid reducing the total number of clusters available for analysis.

The percentage of missing data for the primary outcome of antibiotic prescribing proportion is expected to be low as this will be registered at the first contact consultation. In our previous ERNIE2 trial, we found 4% of missing data for the primary outcome of antibiotic prescribing proportion. Multiple imputation will be considered for the primary outcome measure as well as missing values for patient-reported outcomes (if there are any). Other outcomes will be collected from the patient health record of the physician.

Multiple imputation will be applied to deal with missing data. Imputation will be performed for the binary outcome variable and logistic regression will be used as imputation model. Predictors for the imputation model are baseline patient characteristics and intervention.

2. ARON App Data

A substantial drop-out rate in app completion is anticipated, with non-completion of the app not considered grounds for exclusion from the study. To address this, proactive measures were introduced to enhance participation rates, such as the provision of information about the smartphone app and instructions on installation to children and their parents during the baseline consultation. Additionally, the app was made available in three languages (Dutch, French, English).

Multiple imputation will be applied to deal with missing data. For imputation of continuous variables, a linear regression model will be employed, with baseline patient characteristics and intervention serving as predictors for the imputation model.

3. Administrative Data

Multiple imputation, following Rubin's rules, will be utilized to address missing data. Predictors for the imputation model will include baseline patient characteristics and the intervention.

4. Interview Transcripts

Imputation techniques are not applicable in this dataset.

Statistical Methodology

Statistical Procedures

-

Baseline characteristics & Clinical features

Presentation of baseline characteristics of the study population and comparability of the two arms will be based on the following variables:

- Age (median and 25-75 percentiles)
- Gender (percentage)

Baseline characteristics and clinical features will be reported using frequencies and percentages, means and standard deviations or medians and interquartile ranges, and minimum / maximum, as appropriate.

Primary endpoint

For the analysis of the primary outcome, we will use a mixed-effects logistic regression analysis to account for the clustering at practice level. The child's age and study arm will be included as predefined covariates in the model. We will do this using R software using the 'glmer' function of the 'lme4' package. Results will be reported by an odds ratio (OR) with 95% confidence intervals.

Multiple imputation will be applied to deal with missing data. Ten complete datasets will be constructed and analysed. The 10 results will be combined into a final result following Rubin's rule.

We will analyse the primary endpoint according to the intention-to-treat (ITT) approach, given the pragmatic nature of our trial.

The participating physicians were asked to recruit children with an acute illness consecutively. GPs were likely to have breached the assumption of consecutive inclusions if they:

- recruited fewer than 10 patients per year;
- performed a POC CRP test on nearly all (>90%) of the included children; and/or
- included nearly exclusively children (>90%) based on a negative result on all three items of the clinical decision tree that do not need antibiotics and exclude those that might need antibiotic treatment.

Apart from the intention-to-treat analysis, a per protocol sensitivity analysis will be performed only considering physicians who have recruited children consecutively.

Secondary endpoint – Proportional measures

We will provide a descriptive analysis of the proportion of subjects with the outcome of interest for each randomization group.

A mixed-effects logistic regression model will be employed to address clustering at the practice level. The child's age and study arm will be included as predefined covariates in the model. Odds ratios, along with their corresponding 95% confidence intervals will be reported.

Null hypothesis. The diagnostic algorithm including a standardized clinical assessment, a POC CRP test and safety netting advice is inferior to usual care in terms of the number of days until subjects reach full clinical recovery.

Analysis. We will conduct a descriptive analysis to determine the median time to recovery for each randomization group. IQR will also be provided for each group.

For graphical representation, Kaplan-Meier curves will be generated. These curves will be used in combination with a log-rank test to compare the survival curves of the randomization groups.

Additionally, will employ a mixed-effects Cox regression model to address clustering at the practice level. The child's age and study arm will be included as predefined covariates in the model. Hazard ratios, along with their corresponding 95% confidence intervals, will be reported.

Exploratory endpoints – Proportional measures

We will provide a descriptive analysis of the proportion of subjects with the outcome of interest for each randomization group.

A mixed-effects logistic regression model will be employed to address clustering at the practice level. The child's age and study arm will be included as predefined covariates in the model. Odds ratios, along with their corresponding 95% confidence intervals will be reported.

••

Exploratory endpoints – Satisfactory measures

Statistical analysis not applicable due to the qualitative nature of the data.

Upon transcription of the interviews verbatim, an inductive thematic analysis approach is employed to analyse the data. The entire data analysis process was facilitated using qualitative data analysis software QSR NVIVO software version 12 (QSR International Pty Ltd, Melbourne, Australia).

Findings will be centred on main themes and subthemes closely aligned with the research inquiries and reflective of the interview content. In addition, illustrative quotes will be included.

Exploratory endpoints - Cost-effectiveness of the intervention

Different types of economic evaluations will be conducted to compare participants in the intervention group with those in the control group:

- **Costing study** to comprehend the overall cost structure, identify significant cost drivers, and compare the cost impact.
 - Calculation of costs: In both study groups, the subcategory costs and total costs per patient will be calculated. These costs include the direct medical costs of healthcare use, the cost of the intervention itself, and the indirect costs for patients.
 - Between-group differences: Differences between the intervention and control groups will be calculated for each subcategory and total costs.
 - Descriptive Statistics: Initial assessment of cost difference will involve descriptive statistics to provide unadjusted information regarding the magnitude and distribution of the costs. T-tests and Mann-Whitney U tests will be employed to assess differences between the randomization groups.
 - Generalized Linear Modelling: To evaluate total cost differences between both groups while adjusting for independent factors such as patient characteristics (age and gender).
- Cost-consequences analysis:
 - Compares costs and consequences, encompassing hospitalizations, consultations, pharmaceuticals, and productivity between intervention and control group.
 - Considers perspectives from healthcare payers and society.
 - Utilizes decision-analytic modelling, employing a combination of decision trees and Markov models to track hypothetical cohorts over time.
 - The results of this analysis will be presented as incremental cost-effectiveness ratios, calculated based on natural effects. In case of a dominant or dominated intervention, net benefits will be computed and plotted on a net benefit plot.
- Cost-utility analysis:
 - Compares costs and 'utilities' (calculated using HRQoL data collected through questionnaires in ARON app and the Belgian value set for the EQ5D-Y questionnaire) between intervention and control group.
 - Considers perspectives from healthcare payers and society.
 - Utilizes decision-analytic modelling, employing a combination of decision trees and Markov models to track hypothetical cohorts over time.
 - The results of this analysis will be presented as incremental cost-utility ratios, calculated based on Quality-Adjusted Life Years (QALYs). In case of a dominant or dominated intervention, net benefits will be computed and plotted on a net benefit plot.

We will perform one-way, multi-way, and probabilistic sensitivity analyses, including Monte Carlo simulation and non-parametric bootstrapping, to account for various sources of uncertainty. The outcomes of these analyses will be depicted using cost-effectiveness acceptability curves.

Subgroup Analysis

Subgroup analysis will be performed in order to investigate how the primary outcome behaves in function of:

- Age categories: 0-1 years old, 2-6 years old, 7-12 years old
- Gender: male, female, prefer not to say

Presentation of Results

Figure 1. Flowchart of inclusions/exclusions.

Table 1. Demographic background data, potential predictors, and outcomes (n=x)

Characteristic	Mean +-SD; r	Mean +-SD; median [IQR]; event(yes)/n (percentage)		
	Total	Control	Intervention	

Table 2. Odds ratios with 95% CI and p-value of the treatment effect (n=x)

Outcome	OR (95 %CI)	P-value

Supplementary Tables. Subgroup and sensitivity analyses

Outcome OR (95 %CI) P-value		0		 ,	
	Outcome		OR (95 %CI)		P-value

Rationale for any deviation from pre-specified analysis plan

Not applicable.

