11.3.2 Primary outcome analysis

The primary endpoint will be analyzed according to the intent-to-treat (ITT) approach.

We will use a mixed-effects logistic regression analysis to account for the clustering at practice level, and other potential interaction terms, such as the child's age.

Multiple imputation will be applied to deal with missing data. Imputation will be performed for the binary outcome variable and logistic regression will be used as imputation model. Predictors for the imputation model are baseline patient characteristics and intervention.

Subgroup analysis will be performed in order to investigate how the primary outcome behaves in function of:

- age categories
- gender

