11.3.3 Secondary outcome analysis

We will use a mixed-effects logistic regression analysis to account for the clustering at practice level, and other potential interaction terms, such as the child's age.

Multiple imputation will be applied to deal with missing data. Imputation will be performed for the binary outcome variable and logistic regression will be used as imputation model. Predictors for the imputation model are baseline patient characteristics and intervention.

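### Missing binary outcomes are imputed without practice but analysed with a practice random intercept, so the pooled confidence interval is too narrow: by about 3.5% for the primary outcome at the expected missingness, and by more if follow-up data are lost

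*SAP*

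**What the plan says.** **Imputation.** In the SAP, under Handling of missing values and other data conventions (REDCap data), the rule for a missing binary outcome is that "logistic regression will be used as imputation model. Predictors for the imputation model are baseline patient characteristics and intervention". Protocol 11.3.2 has the same rule for the primary outcome ("Imputation will be performed for the binary outcome variable and logistic regression will be used as imputation model"), and Protocol 11.3.3 repeats it for the secondary outcomes ("Predictors for the imputation model are baseline patient characteristics and intervention"). None of these places names practice, a random effect or academic centre.

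**Analysis.** The SAP's Primary endpoint section specifies a "mixed-effects logistic regression analysis to account for the clustering at practice level". On covariates it says: "The child's age and study arm will be included as predefined covariates in the model". The binary secondary outcomes get the same type of model. On pooling: "Ten complete datasets will be constructed and analysed", combined by Rubin's rule.

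**Amount missing.** The SAP and Protocol 11.3.4 expect few missing primary outcomes and cite 4% in the previous trial. No figure is given for the day-30 record data.

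**Predictors available.** Protocol 8.6 and the SAP list age and gender as baseline characteristics. Protocol 11.3.1 also lists ethnicity and parental smoking.

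**The concern.** The unit of randomisation is the practice, and the planned ICC of 0.063 gives a design effect of about 4 at 50 children per practice. Most of the standard error of the treatment effect therefore comes from variation between practices. A child imputed from arm, age and gender alone is given the average risk for the arm, whatever the practice's own prescribing level. Each such child pulls the practice towards the arm mean. The mixed model then estimates too small a between-practice variance, and the extra between-imputation variance in Rubin's rule does not make up the loss.

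The error is in the anti-conservative direction. For the primary outcome it overstates precision. For the secondary outcomes, Protocol 11.1.1 declares non-inferiority when the upper 95% limit lies below the margin, so an interval that is too narrow favours a non-inferiority claim. Protocol 4.1 wants these same outcomes weighed against any fall in prescribing.

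**Working it through.** **1. The plan's own figure.** Inputs from the SAP's R command: 20.65% vs 14.35%, 50 per practice, ICC 0.063, two-sided alpha 0.05, power 0.90.
- Design effect: 1 + 49 × 0.063 = 4.087.
- Variance sum: 0.2065 × 0.7935 + 0.1435 × 0.8565 = 0.2868.
- Practices per arm: 10.507 × 0.2868 / 0.063² × 4.087 / 50 = 62.05, so 63, as stated. 6300 / 0.9 = 7000, as stated.

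**2. Approximate formula.** Let f be the missing fraction, m the practice size and ρ the ICC. Variances are in units of p(1−p)/n.
- Recorded outcomes only, scattered missingness: [1 + ((1−f)m − 1)ρ] / (1−f).
- Recorded outcomes only, whole practices missing: [1 + (m−1)ρ] / (1−f).
- Completed data, within-imputation: 1 + (m−1)ρ(1−f)² if scattered, or 1 + (m−1)ρ(1−f) if whole practices are missing.
- Between-imputation term with 10 imputations: 1.1 × f/(1−f).

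*Primary, 4% scattered, m = 50.* The ICC in the completed data is 0.063 × 0.96² = 0.058. Completed: 1 + 49 × 0.058 = 3.845. Recorded only: (1 + 47 × 0.063)/0.96 = 4.126. SE ratio √(3.845/4.126) = 0.965. Adding 1.1 × 0.04/0.96 = 0.046 gives 0.971.

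*Secondary, ρ = 0.025 (Protocol 11.1.1), m = 57 (7000/122).*
- 10% scattered: (2.134 + 0.122)/2.508, SE ratio 0.948.
- 10% of practices missing: (2.260 + 0.122)/2.667, SE ratio 0.945.
- 20% of practices missing: (2.120 + 0.275)/3.000, SE ratio 0.894.

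**3. Simulation, primary outcome.** 2000 trials per scenario, 63 practices of 50 per arm, 20.65% vs 14.35%, with the logit random-intercept SD set to 0.673 to give ICC 0.063. Analysis was by random-intercept logistic model, with 10 imputations and Rubin's rules. Age and gender were left out. Missingness is scattered at random.

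| Missing | Method | Mean SE | SE / true SD | Coverage |
|---|---|---|---|---|
| 4% | Recorded outcomes only | 0.1402 | 0.996 | 94.8% |
| 4% | Imputation without practice | 0.1355 | 0.967 | 93.9% |
| 4% | Imputation with practice random intercept | 0.1403 | 0.995 | 94.7% |
| 10% | Recorded outcomes only | 0.1415 | 0.993 | 94.6% |
| 10% | Imputation without practice | 0.1302 | 0.927 | 93.1% |
| 10% | Imputation with practice random intercept | 0.1417 | 0.992 | 94.8% |

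Monte Carlo error of coverage is about 0.5 points. Against recorded outcomes, the SE is 3.4% smaller at 4% missing (0.1355/0.1402) and 8.0% smaller at 10% (0.1302/0.1415). A separate simulation under no effect, with 122 practices of 57 at an 18% rate, gives 3.5% (0.1342/0.1391) and 8.5% (0.1283/0.1402).

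At 4% the true spread of the estimate hardly moves (0.1409 vs 0.1401), so the narrower interval is not recovered information. At 4% the estimated between-practice SD falls from 0.664 to 0.634.

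**4. Simulation, secondary outcomes.** 122 practices of 57, ICC 0.025, rates of 8% and 34% (two of the usual-care rates in Protocol 11.1.1), 150 replicates each. SE shortfall: about 5 to 6% with 10% scattered, about 5.5% with 10% of practices missing, and about 11% with 20% of practices missing. The formula in step 2 gives 5.2%, 5.5% and 10.6%.

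**5. Bias.** At 4% scattered, bias in the log odds ratio is negligible with or without imputation (0.000 vs −0.003). If missingness is assumed to follow the practice's prescribing level in the intervention arm only, the bias is −0.029 with the planned imputation. It is −0.012 both with recorded outcomes only and with two-level imputation.

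**The case against.** The strongest reply is about size. At the only missingness figure in the documents, 4%, the primary result hardly changes: coverage drops by less than 1 point. That stands, and on the primary outcome alone this is a small correction.

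The text also does not forbid a practice term, and the SAP says in one place that imputation is to be considered and in another that it will be applied. But the predictors are listed, practice is not a patient characteristic, and the software section names no multilevel imputation routine.

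Loss of whole practices is not predicted anywhere. Protocol 8.7 offers flying-nurse support for the day-30 form, Protocol 8.10.4 asks for lost data to be recovered through the physician, and Protocol 10 has monthly remote contact. This is why the follow-up scenarios are labelled assumptions. Because the participating physician completes the form, clustered loss is plausible, but no more than that.

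A reader might go further in three ways that the documents do not support:
- **Imputation adds nothing and removes no bias.** Gender is an imputation predictor but not an analysis covariate, and Protocol 11.3.1 lists two more variables. Their contribution was not simulated. Only a small gain is likely.
- **Type I error is clearly inflated at 4% missing.** In the simulation under no effect (700 replicates) it went from 6.0% to 6.6%, with a Monte Carlo error of about 1 point. The SE shortfall is clear; the change in error rate is not.
- **Follow-up outcomes lose 8% and 16% of their SE with 10% and 20% of practices missing.** Those figures come from ICC 0.063 and an 18% rate, which belong to the primary outcome. The plan's ICC for the secondary outcomes is 0.025.

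**Conclusion.** The stated imputation model is incompatible with the stated analysis model, and the interval it produces is too narrow. For the primary outcome the SE is about 3.5% too small at 4% missing, with less than 1 point of coverage lost, and about 8% too small at 10%. For the record-based secondary outcomes it is about 5.5% too small with 10% missing, whether scattered or by practice, and about 11% too small with 20% of practices missing.

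These sizes rest on the planned ICCs and on equal practice sizes. The amounts above 4% and the missingness patterns are assumptions. The conclusion is not that the primary result would be unreliable. It is that the rule costs precision that the trial does not have, for little likely gain, and that the non-inferiority conclusions are the more exposed.

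**What to change.** In the SAP (Handling of missing values, REDCap data, and Primary endpoint) and in Protocol 11.3.2 and 11.3.3, replace the imputation model with a two-level logistic model that has a practice random intercept plus arm, age and gender. An equally valid alternative is to fit the planned mixed model to the children with a recorded outcome. Either choice also settles whether imputation is considered or applied.

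Two additions are optional: the index prescription as a predictor for follow-up outcomes, and the recorded decision-tree items. The latter are entered on the same form as the prescription and may be missing with it, so their value is not established.

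The cost is new wording and a different imputation routine. At the expected missingness the primary interval becomes 3 to 4% wider: its half-width on the log odds ratio goes from 0.2657 to 0.2750, a factor of 1.035.
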